11.1.2. Primary Efficacy variable

The primary efficacy variable will be analyzed using the FAS.

The proportions of patients who reached complete eschar removal at the end of the topical agent soaking period will be compared using logistic regression. The primary analysis will be based on the binary variable (yes/no): 'has complete eschar removal been achieved in all TWs' and will compare NexoBrid with the Gel Vehicle (for further definition and explanation of complete eschar removal see Section 1.1 of the protocol and Section 10.3.2 of this SAP). For handling of missing data see Section 10.1.1. The statistical test will be based on Fisher's exact test because of the small numbers expected in the Gel vehicle group. The odds ratio of achieving complete eschar removal for NexoBrid versus Gel Vehicle and its 95% confidence interval will be estimated using exact distribution methods and will be displayed as shown in Table 6. Bar plots will be shown for the proportions of patients who reached complete eschar removal.

If numerically possible, the comparison will supportively be adjusted for the stratification factor wound depth (all TWs full thickness, mixed TWs, all TWs deep partial thickness) by including

the factor in a logistic regression model together with the treatment variable (NexoBrid vs. Gel Vehicle). Similarly, if convergence of the estimation procedure can be obtained, then, in two other supportive analyses, the factor “Total %TBSA per patient” and the factor treatment center group (see Section 13.8.5 of the protocol as well as Section 11.1.7 of this SAP) will be included in a logistic regression model with the treatment variable. Statistical inference will be based upon exact distribution methods using the “exact” statement in the SAS procedure PROC LOGISTIC. The estimated regression coefficients of the regression analyses will be presented as displayed in Table 7.

The odds ratio of achieving complete eschar removal for NexoBrid versus Gel Vehicle will be estimated from these supportive models, as well as 95% confidence intervals and the level of statistical significance. The results will be displayed as shown in Table 6.

The primary efficacy analysis will be repeated on a wound level as an additional analysis using a mixed logistic regression model with a random effect for patient.

Furthermore, as an additional sensitivity analysis, the primary analysis will be repeated using the PP as analysis population.

If any of the baseline factors, gender, age, percent SPT area (the area of SPT as a percentage of the total area of all TWs, classified as <25% or ≥25%), time from injury to randomization or number of TWs (1, 2, ≥3) are found to be significantly different between the treatment groups, then, if possible, the factor will be included as an extra adjusting covariate in a supportive analysis of the primary endpoint.

11.1.3. Secondary Efficacy variables

The secondary endpoints will be analyzed as described below and will compare efficacy in the NexoBrid group with the SOC group. Missing data will be handled by the methods described in Section 10.1. All secondary endpoints will be analyzed using the FAS. Sensitivity analyses will include analyzing the endpoints using the PP as analysis population.

11.1.3.1. *Incidence of surgical excision*

This is a binary yes/no variable and the proportion of patients who need excision for eschar removal will be compared using logistic regression. The explanatory variables in the model will include treatment, and the following variables: overall TW depth (all TWs full thickness, mixed TWs, all TWs deep partial thickness), “Total %TBSA per patient” and number of TWs (1, 2, ≥3). The odds ratio of requiring surgery for NexoBrid versus SOC will be estimated from the model, as well as 95% confidence intervals and the level of statistical significance. The results

will be displayed as shown in Table 6 and Table 7. Bar plots will be shown for the proportions of patients who needed excision for eschar removal.

If numerically possible, as a supportive analysis, the variable treatment center will be added into the logistic regression model and the analysis repeated.

As a sensitivity analysis, the logistic regression outlined above will be repeated using the PP as analysis population.

If any of the baseline factors, gender, age, percent SPT area (the area of SPT as a percentage of the total area of all TWs, classified as <25% or ≥25%), time from injury to randomization or number of TWs (1, 2, ≥3) are found to be significantly different between the treatment groups, then the factor will be included as an extra adjusting covariate in the logistic regression model described above as additional analysis.

As supportive analysis, the incidence of surgical excision for eschar removal will be compared between NexoBrid and Gel Vehicle using the same explanatory variables as in the main analysis of this endpoint.

A further supportive analysis will repeat the analysis (NexoBrid versus SOC) as described above, but on a wound level. I.e. a mixed logistic regression model with explanatory variables treatment, TW depth, %TBSA per wound and number of TWs and a random effect for patient will be performed.

11.1.3.2. *Time to complete eschar removal*

Time until complete eschar removal will be defined as the time until complete eschar removal has been achieved at a patient level, i.e. for all TW's of an individual patient. This will be measured as time from the randomization date (hours). For patients who do not reach complete eschar removal, their time will be censored at the last non-missing eschar removal assessment (typically the last debridement procedure). Kaplan-Meier curves will be presented graphically (see Figure 3) and in a table (see Table 8) to display the distribution of time to complete eschar removal under the two treatments (NexoBrid vs. SOC). Median time to complete eschar removal will be estimated for each treatment group with a 95% confidence interval. Additionally, time to complete eschar removal will be analyzed descriptively with number of units, number of missing values, mean, standard deviation, min, max, median and quartiles as presented in Table 4. The treatment groups will be compared using a Cox regression model. The comparison will be adjusted for the explanatory variables overall TW depth (all TWs full thickness, mixed TWs, all TWs deep partial thickness), "Total %TBSA per patient", center group (as defined in Section 11.1.10) and number of TWs (1, 2, ≥3), by

including each of them in the Cox regression model together with the treatment variable (NexoBrid vs. SOC). The results of the regression analysis will be displayed as in Table 7. The treatment groups will be compared by testing the null hypothesis of no difference, comparing the ratio of the estimated treatment coefficient to its standard error to a standard normal distribution.

The Cox Regression analysis outlined above will be performed if the proportional hazards assumption appears to hold. This will be checked by including in the regression model a variable representing the interaction between time since randomization and treatment group. If the coefficient for this time variable is non-significant at the 5% significance level, then the Cox Regression analysis will be adopted. If the time-treatment group interaction is significant, then a generalized Wilcoxon-Gehan test will be performed using the *Wilcoxon* option (also provided by default) in the SAS procedure PROC LIFETEST using the following SAS Code:

```
PROC LIFETEST DATA=burn_data;
  TIME time*status(0);
  STRATA depthgroup numtw tbsagroup centergroup / GROUP = treatment_group;
  RUN;
```

Here *burn_data* is the data set containing all necessary information. The variable *time* is the time to complete eschar removal, *status* is a censoring variable and *depthgroup*, *numtw*, *tbsagroup*, and *centergroup* are the variables, which is adjusted for. *Depthgroup*, *tbsagroup* and *centergroup* are the stratification levels defined in Section 11.1.10 and *numtw* is the number of target wounds (1, 2, ≥ 3).

As sensitivity analysis the procedure outlined above will be repeated using the PP instead of the FAS as analysis population.

Supportive analyses will include adjustment for other baseline variables that are imbalanced (i.e. gender, age, percent SPT area [the area of SPT as a percentage of the total area of all TWs, classified as $<25\%$ or $\geq 25\%$], time from injury to randomization or number of TWs (1, 2, ≥ 3)), and investigating interactions between those variables and the treatment groups. In case the proportional hazards assumption could not be rejected, this will be done by including each of the imbalanced baseline variable as well as the interaction between that variable and the treatment group in a separate cox regression analysis. The results of these analyses will be presented as in Table 7. In case the proportional hazards assumption does not hold, the adjustment for the baseline variables will be done using the following SAS code:

```
PROC LIFETEST DATA=burn_data;
TIME time*status(0);
STRATA depthgroup numtw tbsagroup centergroup gender agegroup sptgroup /
GROUP = treatment_group;
RUN;
```

Here burn_data is the data set containing all necessary information. The variable time is the time to complete eschar removal, status is a censoring variable and depthgroup, numtw, tbsagroup, centergroup, gender, agegroup and sptgroup are the variables, which is adjusted for. Agegroup is the categorical age variable computed in Section 10.1.1.2, depthgroup, tbsagroup and centergroup are the stratification levels defined in Section 11.1.10 and numtw is the number of target wounds (1, 2, ≥ 3).

Another supportive analysis will be the comparison of treatments based on the time of complete eschar removal measured from the date of ICF using the same methods as for the time measured from randomization.

Another supportive analysis will be the comparison of treatments based on the time of complete eschar removal measured from the date of injury using the same methods as for the time measured from randomization.

As an additional analysis, time to complete eschar removal will be compared between NexoBrid and Gel Vehicle using the same explanatory variables as for the main analysis of this endpoint.

11.1.3.3. *Blood loss*

In Section 10.3.3.3 two blood loss estimates are defined. Analyses with both blood loss estimates will be conducted. However, some missing values are expected. The analysis with less missing values will be regarded as more reliable and is therefore considered the main analysis. The other analysis is considered supportive. Both analyses will be conducted as follows:

The measure of blood loss defined in Section 10.3.3.3 will be computed for each patient, and the distribution in the NexoBrid group will be compared with that in the SOC group. Means, standard deviations, medians, and interquartile ranges will be calculated and presented as in Table 4. Furthermore, the blood loss will be described graphically by histograms. The normality of the data will be tested on each treatment group using the Shapiro-Wilk test. If the normal distribution hypothesis is not rejected at the 5% significance level in either group, then differences in distribution between NexoBrid and SOC will be tested using a t-test. If the normal distribution hypothesis is rejected either in the NexoBrid group or in the SOC group, then the

differences in distribution between the treatment groups will be tested using a Mann-Whitney test. The test results will be presented as in Table 7.

As sensitivity analysis, the procedure outlined above will be repeated using the PP instead of the FAS as analysis population.

Supportive analyses will include adjustments for the covariates overall TW depth (all TWs full thickness, mixed TWs, all TWs deep partial thickness), "Total %TBSA per patient", center group (as defined in Section 11.1.10), number of TWs (1, 2, ≥ 3) and number of debridement procedures. This will be done by including these variables in a regression model for blood loss together with treatment group.

If any of the baseline factors, gender, age, or percent SPT area (the area of SPT as a percentage of the total area of all TWs, classified as $<25\%$ or $\geq 25\%$), time from injury to randomization are found to be significantly different between the treatment groups, then the factor will be included as an extra adjusting covariate in a supportive analysis of blood loss (as described in the preceding paragraph).

As an additional analysis, blood loss will be compared between NexoBrid and Gel Vehicle without covariate adjustment (similar to the main analysis of this endpoint).

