7.3.2.2. Secondary target variables

The following secondary endpoints will be evaluated in this study:

Reduction in surgical needs

Reduction of surgical need for excisional eschar removal is measured by an analysis of incidence of surgical eschar removal (tangential/ minor/ avulsion/ Versajet and/or dermabrasion excision).

Earlier eschar removal

The time when complete eschar removal has been achieved will be assessed for each patient on the entire eschar removal period. For definition of complete eschar removal, see Appendix 13.1.1.

Blood loss

Blood loss incurred during the eschar removal procedures will be evaluated. Actual blood loss will be measured by considering the estimated blood loss, changes in Hemoglobin during the eschar removal procedures and the amount of units of blood transfused. Blood loss (Actual Blood Loss, ABL) will be calculated using the following formula [25]:

$$ABL = \frac{EBV * (Hb_{before} - Hb_{after})}{(Hb_{before} + Hb_{after})/2} + V_{WB} + \frac{5}{3} V_{PC}$$

EBV= Estimated blood volume is assumed 70 cm³/Kg

(Hb_{before}- Hb_{after})= Changes in Hb following each eschar removal procedure

V_{WB}= Volume [mL] of whole blood transfused

V_{PC}= Volume [mL] of packed red blood cells transfused.

The ABL will be summed over all procedures carried out to remove eschar, with the Hb measured immediately before each procedure and 4 hours after its completion. The amount of blood transfused will be summed over all transfusions carried out during all debridement procedures and 4 hrs later i.e. the before-after periods that are spanned by these Hb measurements.

Additionally, ABL will also be computed using the formula above, but over the whole eschar removal period (not procedure wise) i.e. the eschar removal process will be considered as one continuous procedure. Therefore, only the Hemoglobin value before the first eschar removal procedure and after the last procedure will be used and all blood transfusions performed between these measurements will be included.

Analyses with both blood loss values will be conducted. However, some missing values are expected. The analysis with less missing values will be regarded as more reliable and is therefore considered the main analysis. The other analysis is considered supportive.

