9.3. Secondary Endpoint: Time to complete eschar removal

The logrank comparison between NexoBrid and SOC in the previous trial yielded an estimated log hazard ratio of -1.37 (hazard ratio of 0.254) with a standard error of 0.28.

Therefore, target log hazard ratio (log HR) is $-1.37 + 0.28/2 = -1.23$ (hazard ratio = 0.29).

The formula for the number of events (successful complete eschar removals) is:

$$d = \frac{4(z_\alpha + z_\beta)^2}{(\log HR)^2}$$

where $z_\alpha = 1.96$ two-sided significance level of 5%; and $z_\beta = 1.28$ for 90% power; For 90% overall power, number of events = 28.

Proportions of events: $p_1 = 0.595$ in NexoBrid and $p_2 = 0.728$ in SOC.

Total number of patients required $n = \frac{2d}{p_1 + p_2} = 44$ (to the nearest even number), 22 in each of the NexoBrid and SOC groups.

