10.1.1.2. Secondary Endpoint: Time to complete eschar removal

The analysis of the secondary endpoint time to eschar removal will compute missing values as censored at the date of the last non-missing eschar removal assessment (typically last debridement procedure).

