10.3.3.2. Secondary Endpoint: Time to complete eschar removal

Information about date will be transformed to time in hours from randomization. Time until complete eschar removal will be calculated as the time (in hours) until complete eschar removal has been achieved for a TW. From these times, time to reach complete eschar removal at a patient level, i.e. for all TW's of an individual patient will be calculated. For wounds/patients that do not reach complete eschar removal, their time will be censored at the last non-missing eschar removal assessment (typically the last debridement procedure).

For further analysis, for patients with at least one early grafted target wound, time to complete eschar removal will also be calculated as above, but taking into account only early grafted wounds. Additionally, for patients with at least one late grafted target wound, time to complete eschar removal will also be calculated as above, but taking into account only late grafted wounds.

Additionally, for patients who had at least one target wound that is found, at least partially, in the anatomical area of the hand, time to complete eschar removal will also be calculated as above, but taking into account only target wounds that are found, at least partially, in the anatomical area of the hand.

For an additional analysis, time to complete eschar removal will be computed as above but in hours from injury.

Furthermore, time to complete eschar removal will be computed as above but in hours from ICF.

The patients' age will be categorized into two categories: "younger than 35 years" and "35 years or older". The number 35 years is found to be the median age of the adult population in the previous study MW2004-11-02.

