10.3.3.3.5. Course of debridement procedure

For the multiple imputation outlined in Section 10.1.1.3 for each patient a categorical variable describing the course of the debridement process will be calculated. The different levels of the variable are defined as:

- Only non-surgical SOC debridement
- Non-surgical SOC debridement followed by surgical debridement
- Only surgical debridement
- Only NexoBrid debridement
- NexoBrid debridement followed by non-surgical SOC debridement followed by surgical debridement
- NexoBrid debridement follow by surgical debridement
- Only Gel Vehicle debridement
- Gel Vehicle debridement followed by non-surgical SOC debridement followed by surgical debridement
- Gel Vehicle debridement followed by surgical debridement

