11.1.8. Handling of Multiple Comparisons

Unless otherwise specified, all statistical tests will be conducted against a two-sided alternative hypothesis, employing a significance level of 0.05. The primary and secondary endpoints of efficacy will be tested in a hierarchy, so as to preserve the nominal significance levels:

1. Primary
2. Incidence of surgery
3. Time to complete eschar removal
4. Blood loss.

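### Confirmatory test 3 censors patients known not to have reached complete eschar removal as if they were lost to follow-up, and the SAP is inconsistent on how many such patients to expect

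*SAP*

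**What the plan says.** SAP 11.1.3.2 defines the time from randomization until all target wounds of a patient are cleared. For patients who do not get there, "their time will be censored at the last non-missing eschar removal assessment (typically the last debridement procedure". Section 10.3.3.2 repeats the rule for wounds and patients: "For wounds/patients that do not reach complete eschar removal, their time will be censored at the last non-missing eschar removal assessment". Section 10.1.1.2 presents it as missing-data handling: the analysis "will compute missing values as censored at the date of the last non-missing eschar removal assessment".

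These times feed the Kaplan-Meier medians and an adjusted Cox model. If the time-by-treatment interaction is significant, a stratified Wilcoxon-Gehan test replaces the Cox model. In the hierarchy of 11.1.8 the endpoint is "3. Time to complete eschar removal", after the primary endpoint and incidence of surgery.

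On the period covered, 7.3.2.2 says: "The time when complete eschar removal has been achieved will be assessed for each patient on the entire eschar removal period". Several places foresee further procedures after the topical step. The courses listed in 10.3.3.3.5 include "NexoBrid debridement followed by non-surgical SOC debridement followed by surgical debridement"; Table 1 in 7.2 has a column for standard-of-care procedures that includes additional ones in the topical arms; and 10.3.4.4 names surgical and non-surgical rescue there.

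The sample-size section 9.3 uses: "Proportions of events: $p_1 = 0.595$ in NexoBrid and $p_2 = 0.728$ in SOC". Section 9.1.1 gives the same 0.595 as the earlier trial's NexoBrid rate for the primary endpoint, which is judged at the end of the topical soaking period.

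**The concern.** A patient whose eschar removal has ended without complete removal has a known outcome. Censoring at the last procedure turns that outcome into an unknown one. All three methods then treat the patient as exchangeable with those still at risk, so the estimate assumes eventual clearance at their rate. This is informative censoring. If failures in one arm stop earlier than in the other, they leave the risk set earlier and that arm looks faster than it was.

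Section 7.1.4.1 describes one route that exists only in the topical arms. Its stopping rules apply to NexoBrid and Gel Vehicle, and where eschar removal is discontinued under them, the missing time to its end is handled as missing data. Under 10.1.1.2 a patient without a completion time is then censored at the last assessment. The SAP does not say how often this is expected.

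No planned analysis tests the rule. The per-protocol repeat, the time origins at consent and at injury, and the extra covariates all leave it in place. At stake is the confirmatory claim of earlier eschar removal against standard of care (SOC), and passage to the blood-loss test that follows it.

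**Working it through.** **1. The plan's own figures (9.3).** Inputs: log hazard ratio −1.23, z-values 1.96 and 1.28, event proportions 0.595 and 0.728.

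- Events: 4 × (1.96 + 1.28)² / 1.23² = 41.99 / 1.513 = 27.8, so 28. Reproduced.
- Patients: 2 × 28 / (0.595 + 0.728) = 42.3; rounding each arm up gives 22 + 22 = 44. Reproduced.
- With 75 per arm, expected events are 75 × 1.323 = 99. Power is not the issue.

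**2. What those proportions imply.** Without the event: 1 − 0.595 = 40.5% on NexoBrid and 1 − 0.728 = 27.2% on SOC, or about 30 and 20 of 75. On these figures censored patients are not rare in either arm.

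**3. Which rate is 0.595?** Section 9.1.1 uses it for clearance by the topical step. Section 7.3.2.2 counts clearance over the whole period, in which rescue can add to it. Either 9.3 reuses a topical-step rate for a whole-period endpoint, or clearance by rescue is not meant to count. The SAP never says outright. The SOC figure of 0.728 has no topical-only reading.

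**4. Simulation.** 75 v 75 patients, 400 runs per cell, unstratified Cox/log-rank and Gehan. Assumptions not in the SAP: NexoBrid assessed 8 to 30 h after randomization; median time of SOC patients who clear 48, 96 or 168 h; horizon 28 days. The SOC share cleared is 0.728. A hazard ratio above 1 means faster clearance on NexoBrid; the SAP's 0.29, read in line with the study objective, runs the other way (1/0.29 = 3.4).

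*(a) Rescue clearance not an event, or treatment ends after the topical step.* Each cell gives results for SOC medians 48 / 96 / 168 h.

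| NexoBrid share cleared | HR, failures censored at topical assessment | HR, failures held to day 28 |
|---|---|---|
| 0.595 | 5.51 / 14.40 / 28.81 | 1.00 / 1.11 / 1.14 |
| 0.40 | 3.52 / 9.03 / 18.50 | 0.52 / 0.56 / 0.57 |
| 0.10 | 0.71 / 1.47 / 3.24 | 0.09 / 0.09 / 0.09 |
| 0.05 | 0.32 / 0.73 / 1.58 | 0.04 / 0.04 / 0.04 |

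At 0.595, log-rank rejection in favour of NexoBrid falls from about 100% to 3 / 8 / 13%; Gehan, which weights early times, falls from about 100% to 31 / 69 / 74%. At 0.40, NexoBrid wins by log-rank in 97 / 100 / 100% of runs under the rule. With failures held at risk, SOC is significantly better in 82 / 70 / 69%.

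*(b) Rescue clearance counted, topical share 0.595.*

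- If 72.8% of rescued and of SOC patients clear, the HR is 1.91 / 2.23 / 2.35. Never cleared: 0.405 × 0.272 = 11.0% v 27.2%.
- If 98% clear, the HR is 1.62 / 1.89 / 2.04. Never cleared: 0.405 × 0.02 = 0.8% v 2%.

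These runs were not repeated with failures held at risk. In the 98% case the rule can do little because hardly anyone is left to censor.

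**The case against.** The strongest reply is that the endpoint does not end with the topical step. It covers the entire eschar removal period, rescue is foreseen, and 7.1.4 keeps patients removed from study treatment on follow-up under standard of care. Section 10.3.3.3.1 describes the last procedure as the one that achieved complete debridement, 13.1.1 ties complete removal to the end of the eschar removal phase, and 2.1 says untreated eschar sloughs in about two weeks. On that reading a topical failure is normally cleared later and counts as an event, and 0.595 in 9.3 is a reused planning figure. This stands as an argument about size: the large contrasts in part (a) are conditional. It does not remove the rule, which is written for patients who do not reach complete removal, nor the SOC figure of 0.728.

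Four stronger readings are tempting and are not supported:

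- *A failed NexoBrid patient leaves the risk set within about a day.* No section says so, and the whole-period definition and rescue procedures speak against it.
- *NexoBrid wins whatever share it clears.* Even in part (a) the HR is 0.32 and 0.71 at shares 0.05 and 0.10 with a 48 h SOC median.
- *Only this endpoint lacks a sensitivity analysis for missing outcomes.* Time to wound closure (10.1.2.1) has the same one-sentence rule, and blood loss (10.1.1.3) has no alternative missing-data assumption.
- *The earlier trial's hazard ratio (1/0.254 = 3.9-fold) came from such censoring.* Those data are not available, and genuinely earlier clearance gives the same pattern.

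**Conclusion.** The point holds in a limited form. Test 3 censors known failures as if their outcome were missing, this is informative, and nothing planned would reveal its effect. The size cannot be fixed from the SAP, because whole-period assessment in 7.3.2.2 and the 0.595 in 9.3 do not fit together. If clearance by rescue is not an event, or treatment ends after the topical step, the rule could turn near-equality into an overwhelming win. If rescue counts and nearly all patients clear, the effect is small.

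The simulated sizes rest on assumed procedure times, a 28-day horizon and unstratified tests, whereas the SAP plans an adjusted Cox model or a stratified Wilcoxon test. They show what the rule can do and do not forecast this trial's result.

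**What to change.** - In 10.1.1.2, 10.3.3.2 and 11.1.3.2, state that clearance by any procedure in the eschar removal period is an event, in line with 7.3.2.2.
- Censor at the last assessment only patients lost or withdrawn while eschar removal is ongoing.
- Keep patients whose eschar removal ended without documented complete removal at risk, without an event, to one common horizon in both arms. Fix it before unblinding, no earlier than the longest observed eschar removal time. Kaplan-Meier, Cox and Gehan use risk sets only at event times, so any horizon beyond the last event gives the same result.
- Show cumulative incidence of complete eschar removal by arm.
- Report the present censoring rule as a sensitivity analysis.
- In 9.3, reconcile p1 = 0.595 with the whole-period definition, and restate it if it is the topical-step rate.

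The cost is SAP wording and one derivation rule, with no new data. The downside for the sponsor is that the hazard ratio may become less favourable.

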9.3.1. Summary of sample size

Although the maximum sample size from the above calculations is a total of 121 patients (65 in the NexoBrid group, 13 in the Gel vehicle group and 43 in the SOC group (to match NexoBrid numbers)), we propose entering larger numbers to provide an extra margin of assurance in achieving positive results on the efficacy outcomes, and adequate information on safety outcomes to allow better benefit vs. risk assessment.

Therefore, we plan a study with total sample size of 175 patients; 75 (NexoBrid) + 75 (SOC) + 25 (Gel Vehicle).

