11.1.7. Multicenter Data

Randomization will be stratified by center group as detailed in the Section 13.7.2 of the protocol.

The analyses of the primary and secondary endpoints of this trial will adjust for possible effects of the variable center by including it as covariate in the analyses.

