11.1.10. Stratification

The following factors are used to stratify the study design:

A. Total TBSA % per patient

A1: Total TBSA <=15%

A2: Total TBSA >15%

B. Overall depth per patient

B1: All TWs are full thickness;

B2: Mixed TWs – full thickness and deep partial thickness

B3: All TWs are deep partial thickness.

C. Center Group, to address possible differences in SOC procedures between sites (if any), to allow comparison of the results within group of centers and to reduce the likelihood of a group of centers including patients in only one arm of the study (5 groups of centers were formed based on similarity of SOC practice).

These factors are accounted for in the analyses of the primary and secondary endpoints by including them as adjusting variables.

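### The confirmatory fallback test for time to complete eschar removal splits 150 patients over 90 strata, with no rule for sparse cells

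*SAP*

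**What the plan says.** Section 11.1.3.2 first plans a Cox model adjusted for overall target-wound depth, total %TBSA, center group and number of target wounds. If the time-by-treatment interaction is significant at 5%, a Wilcoxon-Gehan test in PROC LIFETEST takes its place, with the statement "STRATA depthgroup numtw tbsagroup centergroup / GROUP = treatment_group".

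Section 11.1.10 lists the stratification factors of the design: TBSA (2 levels), depth (3) and center group (5). Of these it says "These factors are accounted for in the analyses of the primary and secondary endpoints by including them as adjusting variables". Section 11.1.7 says that the primary and secondary analyses "will adjust for possible effects of the variable center by including it as covariate in the analyses". Number of target wounds (1, 2, 3 or more) is not a stratification factor.

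Section 11.1.8 places this endpoint third, after the primary endpoint and incidence of surgery and before blood loss; these endpoints "will be tested in a hierarchy, so as to preserve the nominal significance levels".

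For the supportive analyses, the text of 11.1.3.2 says "Supportive analyses will include adjustment for other baseline variables that are imbalanced", and the Cox branch fits each such variable in a separate model. The matching LIFETEST code, however, has "STRATA depthgroup numtw tbsagroup centergroup gender agegroup sptgroup", which lists gender, age group and SPT group together.

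**The concern.** In a Cox model, number of target wounds costs two parameters. In a fully crossed stratified rank test it triples the number of cells, from 30 to 90. With 150 patients many cells will hold one patient, or patients from one arm only. Those patients still appear in the Kaplan-Meier curves and descriptive tables but carry no weight in the test.

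The fallback is a realistic branch:

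- Topical success is judged within hours of starting treatment (Section 10.1.1), and NexoBrid patients without complete removal may go on to surgical or non-surgical debridement (Section 10.3.3.3.5). An early burst of events followed by an SOC-like course is not proportional.
- The planning figures in Section 9.3 point the same way. They pair a hazard ratio of 0.29 in favour of NexoBrid with "Proportions of events: $p_1 = 0.595$ in NexoBrid and $p_2 = 0.728$ in SOC". Under proportional hazards and equal follow-up, 0.728 in SOC would imply 1 − 0.272^(1/0.29) ≈ 0.99 in NexoBrid. Unequal censoring could also explain the gap.

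At stake is power for the third confirmatory test and, through the hierarchy, access to the blood-loss test.

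**Working it through.** **The plan's own figure.** Section 9.3: d = 4(1.96 + 1.28)² / 1.23² = 27.75, so 28 events, as stated. Patients: 2 × 28 / (0.595 + 0.728) = 42.3; the SAP states 44, the next even number up. The endpoint is generously sized at 150.

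**Cell counts** (levels from 11.1.3.2 and 11.1.10, patients from 9.3.1)

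- Confirmatory fallback: 3 × 3 × 2 × 5 = 90 cells; 150 / 90 = 1.7 patients per cell.
- Randomisation strata: 3 × 2 × 5 = 30 cells; 150 / 30 = 5 per cell.
- Supportive code: 90 × 2 × 2 × 2 = 720 cells.

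**Why a one-arm cell drops out.** At each event time a stratum contributes n(d₁ − d·n₁/n) to the statistic, and its variance term is proportional to (n₁/n)(1 − n₁/n). Here n is the number at risk, d the number of events, and the subscript 1 marks one arm. If only one arm is present, n₁ = n or n₁ = 0, and both terms are zero.

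**Simulation assumptions** (the SAP gives none of these)

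- 175 patients, 3:3:1, permuted blocks of 7 within the 30 strata; NexoBrid and SOC analysed.
- Margins even; moderate (depth 15/35/50%, wounds 40/30/30%, TBSA 75/25%, center groups 30/25/20/15/10%); or skewed (10/30/60, 55/30/15, 85/15, 40/25/15/12/8). For 720 cells: gender and age 50/50, SPT group 30/70.
- SOC times Weibull, shape 1.5, median 96 h; fast finishers uniform over 6–30 h. Factors either not prognostic, or with log-hazard effects of ±0.4 (depth), ±0.6 (center), ±0.3 (wounds) and ±0.2 (TBSA).
- 1,500 replicates (standard error at most 1.3 points); 300 for the proportional-hazards check and two-step power.

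**Patients in one-arm cells:** 2.5–6.0% with 30 strata, 21–36% with 90, 69–87% with 720. A separate run of 3,000 replicates gave 20–36% against 2.5–6% for similar margins. Adding unblocked allocation and a more extreme skew widened this to 16–43% against 2.5–9%.

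**Power of the fallback test under non-proportional hazards**

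| Scenario | 30 strata | 90 strata | PH check rejects |
|---|---|---|---|
| (a) Events 59.5% / 72.8% (9.3), NexoBrid events early, rest censored | 97–99% | 85–95% | 99–100% |
| (b) 56.65% finish fast (9.1.1), rest like SOC, no censoring | 99–100% | 93–97% | 80–93% |
| (c) 40% finish fast (hypothetical, not in the SAP) | 86–92% | 66–81% | 54–71% |

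In (c) the whole two-step procedure falls from 87–92% to 76–85%.

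**Constant hazard ratio 0.29.** The check rejects in only 7–9% of trials, so Cox is normally used. The 90-strata test would keep 98–99% power without censoring, and 81–91% with the 9.3 event proportions and early censoring.

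**Type I error:** 5.0–5.8% with 30 strata, 4.9–5.4% with 90. A 600-run simulation with exponential times gave one outlying value, 8.8% with 30 strata; repeating that design with 6,000 runs gave 4.9–5.3% with 30 strata and 4.6–5.1% with 90.

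**The case against.** The strongest reply is that the consequence is small under the planned effect. Section 9.3 needs 44 patients and 150 are planned. In (b), power stays above the 90% design target even with 90 strata, and type I error is sound.

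Scenario (a) can also be questioned. The endpoint covers the whole eschar-removal period (Section 7.3.2.2), so patients in whom topical treatment fails can still have an event, and 0.595 is also the topical-only success proportion in Section 9.1.1. That makes (b) the closer picture, although Section 9.3 does state 0.595 for this endpoint. Scenario (c) is hypothetical.

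Including number of target wounds is also coherent. The endpoint is time until all wounds are clear, the Cox branch adjusts for the same four factors, and Sections 11.1.3.1, 11.1.4.1 and 11.2.4.2 adjust for it too. Sections 11.1.7 and 11.1.10 do not contradict the code, since all three randomisation factors are in it. A pooling order would keep the covariate set. Nor are 30 strata free: one set of runs of (c) gave 96–97% power unstratified, 86–91% with 30 strata and 69–76% with 90.

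These points limit the weight of the concern. They do not remove it: 90 strata lost power in every scenario, and the loss can be avoided.

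**Conclusion.** The concern holds. The 90 cells, the 150 patients, the confirmatory status and the absence of a pooling rule are read directly from the SAP. The zero contribution of one-arm cells follows from the test itself. The percentages rest on assumed margins, independence between factors, assumed block size and assumed time distributions.

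This is an efficiency problem, not a validity problem. The loss is small to moderate under the SAP's planned effects (roughly 3–7 points in (b), more in (a)) and larger if the effect is weaker. It arises only when the proportional-hazards check sends the analysis to the fallback. The plan should be changed, but the trial's conclusions are not invalid without the change.

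The 720-cell code is a separate mismatch between text and code. It affects a supportive analysis only and adds no weight to the confirmatory point.

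**What to change.** In Section 11.1.3.2, delete `numtw` from the confirmatory STRATA statement, leaving depth, TBSA and center group: the 30 randomisation strata, in line with 11.1.7 and 11.1.10. Keep the present four-factor code as a supportive analysis and say so in one sentence. In the second code block, add only the covariates found imbalanced, one at a time, as the text and the Cox branch already do.

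The cost is one word of code and a sentence of text; 11.1.7 and 11.1.10 stay as they are. The downside is that the confirmatory fallback no longer conditions on number of target wounds while the Cox branch still does. If the sponsor prefers the same covariates in both branches, the alternative is to keep the factor and fix in advance an order for pooling sparse cells, blind to outcome.
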